7.3. Exploratory Efficacy Analyses

7.3.1. Endpoints / Variables

Incidence of genetically homologous and genetically heterologous *P. vivax* infections (determined by PCR)

Percentage of participants relapsing by CYP2D6 genotype

By metabolizer class

By activity score

7.3.2. Summary Measure

Number and percentage of participants in each category at the end of the study.

7.3.3. Population of Interest

The exploratory efficacy analyses will be based on the microbiologic-Intent-To-Treat population.

7.3.4. Strategy for Intercurrent (Post-Randomization) Events

The summary statistics will be based on available data only.

7.3.5. Statistical Analyses / Methods

Details of the planned displays are provided in [Appendix 11](#): List of Data Displays.

These will be based on GSK data standards and statistical principles.

Unless otherwise specified, endpoints / variables defined in Section [7.3.1](#) will be summarised using descriptive statistics and listed.

Exploratory Statistical Analyses
Endpoint / Variable
Incidence of genetically homologous and genetically heterologous P. vivax infections (determined by PCR) See Section 11.6.3 for derivation of a relapse.
Model Specification
Descriptive statistics only. mITT population
Model Checking & Diagnostics
Only summary statistics are planned for this endpoint therefore no model checking is required.
Model Results Presentation
Summary table (n and %) (Table 2.21) showing the proportion of participants in each treatment group with P. vivax relapse infections classified as genetically heterologous or homologous n will be the number of participants with a relapse Bar chart of the percentage of participants on each treatment arm with genetically heterologous or homologous infections, with 95% Wilson confidence intervals (Figure 2.8)

Exploratory Statistical Analyses
Subgroup Analyses
No subgroup analyses are planned for this endpoint.
Sensitivity and Supportive Analyses
No sensitivity analyses are planned for this endpoint.

Exploratory Statistical Analyses
Endpoint / Variable
Percentage of participants relapsing by CYP2D6 genotype – Metabolizer Class.
Model Specification
mITT population Logistic regression model adjusting for derived CYP2D6 metabolizer class (poor + intermediate combined, or extensive + ultra combined, due to low numbers of poor and ultra metabolisers in the study) within treatment arm (models fitted separately for each treatment arm) One-sided test at the 5% significance level (given published data indicating reduced CYP2D6 metabolism decreases PQ efficacy)
Model Checking & Diagnostics
Goodness of fit tests and residual plots (pearson and deviance residuals to detect outliers and/or influential points) will be produced.
Model Results Presentation
Number and percentage of participants relapse free in each metaboliser class grouping within each treatment arm Adjusted odds ratio, 90% CI and p-value
Subgroup Analyses
No subgroup analyses are planned for this endpoint.
Sensitivity and Supportive Analyses
No sensitivity analyses are planned for this endpoint.

Exploratory Statistical Analyses
Endpoint / Variable
Percentage of participants relapsing by CYP2D6 genotype – Activity Score
Model Specification
mITT population Logistic regression model adjusting for qualitative CYP2D6 Activity Score (AS) within treatment arm (models fitted separately for each treatment arm)
Model Checking & Diagnostics
Goodness of fit tests and residual plots (pearson and deviance residuals to detect outliers and/or influential points) will be produced.
Model Results Presentation
Degrees of freedom, wald chi-square and p-value of the type III effect of AS in the model
Subgroup Analyses
No subgroup analyses are planned for this endpoint.

Sensitivity and Supportive Analyses

No sensitivity analyses are planned for this endpoint.

Additional Efficacy Summaries

P. vivax asexual parasite counts (Table 2.1), mITT population:
Summary statistics (n, median, Q1, Q3, min and max) at each timepoint by treatment group.

Other malarial asexual parasite counts (Table 2.2), *P. vivax* gametocyte counts (Table 2.3), other malaria gametocyte counts (Table 2.4), mITT population:
Summary statistics (n, median, Q1, Q3, min and max) at each timepoint by treatment group.

Summary of participants with *P. vivax* gametocyte emergence post baseline (n, %), mITT population, by treatment group.

Summary of participants with *P. falciparum* asexual parasite emergence post baseline (n, %), mITT population, by treatment group.

Summary of the number of relapses per subject (n, %), mITT population, by treatment group.

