	
 
○ GI tolerability – incidence of abdominal pain, heartburn, diarrhoea, constipation, nausea and vomiting.
 
○ Change from baseline in methemoglobin
 
○ Change from baseline in QTcF
 
○ Incidence of protocol-defined SAEs (i.e. a decrease in hemoglobin of <math>\geq 30\%</math> or <math>>3</math> g/dL from baseline; or, a drop in absolute hemoglobin to <math>< 7.0</math>g/dL, in the first 15 days)
 

 
● To evaluate the pharmacokinetics of tafenoquine when co-administered with DHA-PQP in adult subjects with P.vivax malaria.
 
	
 
● Population PK parameters for tafenoquine including but not limited to oral clearance (CL/F) and volume of distribution (V/F).
 

Exploratory	

 
● To explore the genetics of recurrence of P.vivax malaria.
 
	
 
● Incidence of genetically homologous and genetically heterologous P.vivax infections (determined by PCR).
 
● Whole genome sequencing of multiple parasite genes will be undertaken, if parasite count allows (to be reported separately).
 

 
● To examine the relationship between CYP2D6 genotype and risk of P.vivax relapse.
 
	
 
● Percentage of subjects relapsing analyzed according to CYP2D6 genotype.
 

 
● To explore the relationship between the pharmacokinetics of tafenoquine co-administered with DHA-PQP and pharmacodynamic endpoints (if appropriate).
 
	
 
● Population PK (e.g. tafenoquine plasma concentrations) and selected pharmacodynamic (PD) endpoints (e.g., relapse-free efficacy, change in methemoglobin).
 

With regards to the efficacy endpoints, it should be noted that it is not possible to determine if a subject's recurrence of malaria is a relapse or recrudescence. For the purposes of this protocol, the term "relapse" will be used to describe any recurrence of *P.vivax* malaria after clearance of the initial infection. "Recrudescence" applies to the term relating to recurrence for Days 1-14 of the study, where a genetically homologous

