Number needed to treat per treatment group before one extra
success was seen compared to DHA-PQP only

Xx (xx,xx)

Xx (xx,xx)

[1] Subjects are censored if they did not have *P.vivax* at baseline, or took a drug with anti-malarial action despite not having malaria parasites, or did not have a 6 month assessment.

[2] Kaplan-Meier methodology

[3] Estimated from Cox's Proportional Hazards Analysis, adjusting for Battalion.

A hazard ratio < 1 indicates a lower chance of relapse compared to DHA-PQP only.

Population: Microbiologic Intent-to-Treat

EFF_T3
 Logistic Regression Analysis of Relapse-Free Efficacy at 6 Months (Subjects Censored Prior to 6 Months Excluded)

Treatment Group	N	n	Subjects Relapse Free (%)	Subjects Relapsed (%)	Comparison with DHA-PQP Only		
					Adjusted Odds Ratio of Relapse	95% CI	p-value
TQ+DHA-PQP	Xx	Xx	Xxx (xx%)	Xxx (xx%)	x.xx	(x.xx, x.xx)	0.xxx
PQ+DHA-PQP	Xx	Xx	Xxx (xx%)	Xxx (xx%)	x.xx	(x.xx, x.xx)	0.xxx
DHA-PQP Only	Xx	xx	Xxx (xx%)	Xxx (xx%)			

Note: Model includes terms for battalion and treatment.
 An odds ratio <1 represents a smaller chance of relapse compared to DHA-PQP only.

Population: Microbiologic Intent-to-Treat

TTE3

Analysis of Time to <Asexual Parasite Clearance>

	TQ+DHA-PQP (N=xxx)	PQ+DHA-PQP (N=xxx)	DHA-PQP only (N=xxx)
Number of Subjects			
Relapse	xx (xx%)	xx (xx%)	xx (xx%)
Censored	xx (xx%)	xx (xx%)	xx (xx%)
Estimates for Time to Clearance (Days) [1]			
1st Quartile	xx.x	xx.x	xx.x
95% CI	(xx.x, xx.x)	(xx.x, xx.x)	(xx.x, xx.x)
Median	xx.x	xx.x	xx.x
95% CI	(xx.x, xx.x)	(xx.x, xx.x)	(xx.x, xx.x)
3rd Quartile	xx.x	xx.x	xx.x
95% CI	(xx.x, xx.x)	(xx.x, xx.x)	(xx.x, xx.x)
Adjusted Hazard Ratio vs DHA-PQP only [2]			
Estimate	x.xx	x.xx	
95% CI	(x.xx, x.xx)	(x.xx, x.xx)	
p-value	x.xxx	x.xxx	
Adjusted Hazard ratio vs PQ+DHA-PQP [2]			
Estimate	x.xxx		
95% CI	(x.xxx, x.xxx)		

[1] Kaplan-Meier methodology

[2] Estimated from Cox's proportional Hazards Analysis, adjusting for Battalion.
 A hazard ratio <1 indicates a lower risk of [endpoint] compared to DHA-PQP only.

Population: Microbiologic Intent-to-Treat

EFF_T4

Incidence of Genetically Homologous and Genetically Heterologous *P. vivax* Infections (determined by PCR)

	TQ+DHA-PQP (N=xx)	PQ+DHA-PQP (N=xx)	DHA-PQP only (N=xx)
n [1]	Xx	Xx	Xx
P. vivax classified as genetically heterologous by PCR	Xx (xx%)	Xx (xx%)	Xx (xx%)
P. vivax classified as genetically homologous by PCR	Xx (xx%)	Xx (xx%)	Xx (xx%)

[1] n = number of subjects with an infection

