>30 g/L or >=30%	xx (xx%)	xx (xx%)	xx (xx%)	xx (xx%)

Population: Safety

SAFE_T4
Summary of Time on Treatment Before Liver Event

	TQ+DHA-PQP (N=xx)	PQ+DHA-PQP (N=xx)	DHA-PQP only (N=xx)
Subjects reporting at least one liver event	xx (xx%)	xx (xx%)	xx (xx%)
Subjects with events occurring while receiving study treatment	xx (xx%)	xx (xx%)	xx (xx%)
Subjects with events occurring after stopping study treatment	xx (xx%)	xx (xx%)	xx (xx%)
Time from start of treatment to event (days)			
n	xx	xx	xx
Mean	x.x	x.x	x.x
sd	x.x	x.x	x.x
Median	x.x	x.x	x.x
Minimum	x.x	x.x	x.x
Maximum	xx.x	xx.x	xx.x
Time from most recent treatment to event (days)*			
n	xx	xx	xx
Mean	x.x	x.x	x.x
sd	x.x	x.x	x.x
Median	x.x	x.x	x.x
Minimum	x.x	x.x	x.x
Maximum	xx.x	xx.x	xx.x

* For events which occur during treatment, time from treatment to event is set to one day.

CONFIDENTIAL

200894

Population: Safety

SAFE_T5			
Summary of QTcF Values (msec) by Category and Visit			
Actual Relative Time Result	TQ+DHA-PQP (N=xx)	PQ+DHA-PQP (N=xx)	DHA-PQP only (N=xx)
Maximum post baseline change			
n	xx	xx	xx
Increase 0 - <30	xx (xx%)	xx (xx%)	xx (xx%)
Increase >=30 - <60	xx (xx%)	xx (xx%)	xx (xx%)
Increase >=60 and QTcF <=480	xx (xx%)	xx (xx%)	xx (xx%)
Increase >=60 and QTcF >480	xx (xx%)	xx (xx%)	xx (xx%)
Baseline			
n	xx	xx	xx
<=450	xx (xx%)	xx (xx%)	xx (xx%)
>450 to <=480	xx (xx%)	xx (xx%)	xx (xx%)
>480 to <=500	xx (xx%)	xx (xx%)	xx (xx%)
>500	xx (xx%)	xx (xx%)	xx (xx%)
Day 3			
n	xx	xx	xx
<=450	xx (xx%)	xx (xx%)	xx (xx%)
>450 to <=480	xx (xx%)	xx (xx%)	xx (xx%)
>480 to <=500	xx (xx%)	xx (xx%)	xx (xx%)
>500	xx (xx%)	xx (xx%)	xx (xx%)
Increase 0 - <30	xx (xx%)	xx (xx%)	xx (xx%)
Increase >=30 - <60	xx (xx%)	xx (xx%)	xx (xx%)
Increase >=60 and QTcF <=480	xx (xx%)	xx (xx%)	xx (xx%)
Increase >=60 and QTcF >480	xx (xx%)	xx (xx%)	xx (xx%)

...

Note: If triplicate measurements are reported at a timepoint (as planned on Day 1, and occasionally

CONFIDENTIAL

[figure not shown]
200894

occurring at other visits), the data summarized in the table is the mean of the triplicate measurements.
Note: Day 1 pre DHA-PQP dose is considered as baseline.

Population: Microbiologic Intent to Treat

EFF_F1

Incidence (95% Confidence Interval) of Genetically Homologous and Genetically Heterologous *P. vivax* Infections

[figure not shown]
n = number of *P. vivax* relapses

Bars represent 95% Wilson confidence intervals

Note to programmers: Include Bars for all 3 treatment groups.

Population: Microbiologic Intent to Treat

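### Table 2.21 and Figure 2.8 are titled incidence in mITT, but n is defined from relapsers, so the printed percentages would most naturally be the mix of relapses, not incidence

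*SAP*

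**What the plan says.** Protocol Section 3 lists the exploratory endpoint as "Incidence of genetically homologous and genetically heterologous" infections, determined by PCR. SAP 7.3.3 sets the mITT population for exploratory efficacy. SAP 7.3.2 gives the summary measure as "Number and percentage of participants in each category at the end of the study", without naming a denominator.

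SAP 7.3.5 then points two ways:

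- **Arm as base.** Table 2.21 is described as "showing the proportion of participants in each treatment group with P. vivax relapse infections classified as genetically heterologous or homologous". Figure 2.8 is described as "Bar chart of the percentage of participants on each treatment arm with genetically heterologous or homologous infections", with 95% Wilson intervals.
- **Relapsers as base.** For Table 2.21, "n will be the number of participants with a relapse".

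The shells in SAP Appendix 12 add two more definitions. The Table 2.21 shell (EFF_T4) has "n = number of subjects with an infection", printed directly above the two percentage rows. The Figure 2.8 shell (EFF_F1) has "n = number of *P. vivax* relapses", under a title that says incidence with a 95% confidence interval.

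**The concern.** All three definitions of n point to the people or episodes with a relapse. A programmer working from them would probably divide by n and print the result under an incidence title.

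Relapse is the trial's primary outcome, so that denominator is itself changed by treatment. A share among relapsers describes the genetic mix of the relapses that occurred. It is not a risk, and differences or similarities between arms are not protected by randomisation. A drug that prevents both types equally gives the same bar height as control. A drug that prevents only one type pushes up the share of the other, although the other's incidence has not moved.

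The three definitions are also not interchangeable. SAP 11.6.3 allows a participant more than one relapse, and Table 2.29 counts them, while Protocol 7.4 collects the PCR sample at the first recurrence. A figure based on relapses need not match a table based on participants. EFF_T4 also has no row for relapses without a PCR result, so it is unclear whether these stay in n.

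**Working it through.** **Inputs.** Protocol 9.2.1 gives 50 participants per arm and relapse-free rates of 50% (DHA-PQP alone), 85% (PQ) and 85% (TQ). I take mITT N as 50 per arm. The documents give no homologous share, so I assume 20% to 80%.

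**The plan's own figure.** Expected relapses are 50 × 0.50 + 50 × 0.15 + 50 × 0.15 = 25 + 7.5 + 7.5 = 40, and 40/150 = 26.7%. This agrees with Protocol 9.2.1. The relapser denominators would therefore be about 25 in control and 7.5 in each active arm.

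**Equal homologous share s in both arms.** Among relapsers the percentage is s in each arm. As mITT incidence it is 0.50 × s in control and 0.15 × s on TQ.

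| Assumed s | Share among relapsers, control vs TQ | mITT incidence, control vs TQ |
|---|---|---|
| 20% | 20% vs 20% | 10% vs 3% |
| 40% | 40% vs 40% | 20% vs 6% |
| 50% | 50% vs 50% | 25% vs 7.5% |
| 60% | 60% vs 60% | 30% vs 9% |
| 80% | 80% vs 80% | 40% vs 12% |

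The incidence ratio is 0.15/0.50 = 0.30 in every row. The relapser-based percentages show none of it.

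**Unequal shares.** With assumed shares of 40% in control and 60% on TQ, the relapser display reads 40% vs 60%. The mITT incidence is 0.50 × 0.40 = 20% vs 0.15 × 0.60 = 9%, which is the opposite direction.

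**Whole-number example with Wilson 95% intervals.** Assume 15 homologous of 25 relapses in control and 5 of 8 on TQ.

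- Among relapsers: 15/25 = 60% (41 to 77) vs 5/8 = 63% (31 to 86).
- In mITT: 15/50 = 30% (19 to 44) vs 5/50 = 10% (4 to 21).

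**Do Tables 2.13 and 2.14 supply the same number?** They repeat the primary analysis, censoring the other type when it occurs (SAP 7.1.5.1 and 11.6.3). That estimates net risk. If the type-specific hazards are proportional (assumed) and s = 60%, the net homologous risk in control is 1 − 0.50^0.6 = 34%, against a crude incidence of 30%. On TQ it is 1 − 0.85^0.6 = 9.3%, against 9%. The two are close but are different quantities, so no planned display prints the crude incidence that the endpoint names.

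**The case against.** The case on the other side is substantial, and much of it stands.

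- **The denominator is inferred.** The SAP defines n but never says what the percentage is divided by, and its own descriptions of the table and figure refer to the treatment group and arm. A reader might infer that the SAP fixes relapsers as the denominator. That is the more natural reading given both shells, but the text does not settle it. What the documents do establish is a conflict between title, text and shells.
- **The report does not conceal the effect.** EFF_T4 prints N for each arm and the count of each type, so count/N can be worked out from the table. Tables 2.13 and 2.14 with Figures 2.3 and 2.4 give Kaplan-Meier results by type and arm in mITT, and overall relapse by arm is in Tables 2.5 and 2.8. The risk of misreading is confined to the printed percentages and intervals, mainly in Figure 2.8, where the bars are seen side by side.
- **The mix is wanted.** Protocol 4.1 says genotyping is meant to explore what proportion of relapses is of each type. The relapser share is a legitimate summary and should stay. It needs a title that says what it is.
- **No test is planned.** The display is descriptive and exploratory, so no formal inference is compromised. The arms are still shown beside each other with intervals, which invites comparison.

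**Conclusion.** The point holds as an inconsistency of label and denominator in one exploratory table and one figure. The endpoint and titles say incidence in mITT, while the definitions of n lead most naturally to shares of relapses. Those shares should not be read across arms. At the planning rates, any equal homologous share gives identical relapser-based percentages, while mITT incidence runs from 10% vs 3% (share 20%) to 40% vs 12% (share 80%).

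These sizes rest on the protocol's planning relapse rates, an mITT N of 50 per arm, and homologous shares that are assumptions. That equal shares give equal percentages is arithmetic and does not depend on the value chosen.

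A reader might infer from this that the analysis plan hides a large treatment effect. The documents do not support that, because the counts, arm totals and type-specific Kaplan-Meier analyses are all planned. The primary analysis, alpha and sample size are untouched. This is a minor improvement.

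**What to change.** In SAP 7.3.5, the EFF_T4 shell and the Figure 2.8 shell:

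1. Report incidence as the number of participants whose first relapse is of each type, divided by the arm's mITT N, with Wilson 95% intervals. Describe it as crude incidence, because participants censored early count as event-free.
2. Keep the share among relapsers as a second row, labelled as the distribution among first relapses and not a treatment comparison.
3. Use one definition of n throughout: participants with a first relapse.
4. Add a row for relapses without a PCR classification, and state whether they are in the denominator of the relapser share.
5. Footnote that Tables 2.13 and 2.14 estimate net risk because the other type is censored.

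The cost is a text edit and reprogramming of one table and one figure. No new data are needed.

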- Hemoglobin decreases of  $\geq 30\%$  or  $>3\text{g/dL}$  from baseline or, a drop in absolute hemoglobin to  $<7.0\text{g/dL}$ , in the first 15 days will be reported as a protocol-defined SAE even if asymptomatic and not requiring medical intervention. Blinded study treatment will be stopped immediately if a subject meets the protocol-defined SAE criteria for Hb drop together with clinical or laboratory evidence of hemolysis (refer to Section 5.4.2 and Section 7.5.1.1).

- Exploratory CYP2D6 genotype analyses will be undertaken to test the hypothesis that null and/or intermediate metabolizers of 8-aminoquinoline drugs are more at risk of *P. vivax* relapse with PQ but not TQ [Bennett, 2013].
- The primary analysis population will be the Intent To Treat (ITT) population
- A subject is considered to have completed the double-blind study if they are randomized to blinded study treatment and complete the Day 180 visit.
- Subjects who have not relapsed prior to the Day 180 visit will be given open label PQ 0.5mg/kg daily for 14 days to minimize the likelihood of *P. vivax* recurrence after the end of the study. These subjects will return for a final safety follow up visit 15 days later.
- If it is not possible to completely recruit the study from a single battalion but at least 120 subjects have been randomized, a blinded review of the relapse data will be conducted, with the intention to stop enrolment early if this review predicts that the combined relapse rate will be  $\geq 26.7\%$  at the end of the follow up period (based on sample size assumptions). Kaplan-Meier estimates will be made of the overall six month relapse rate, using all of the data available at that time. If this relapse criterion is met, enrolment will stop and the study will be analyzed once all the existing subjects have completed the 6 months follow up. If the blinded review predicts that the relapse rate will be  $< 26.7\%$ , further subjects will be recruited from a second battalion, up to a maximum of 150 subjects in total (See Section 9.2.3).
- The study design schematic is provided in Figure 1.

Figure 1 200894 Study Design Schematic

Open label DHA-PQP 3 or 4 tablets per day (according to weight) on Days 1-3 plus blinded study treatment as follows:

- 1) Tafenoquine 300 mg single dose on Day 1 and placebo for primaquine on Day 1-14\*
- 2) Primaquine 15mg on Days 1-14 and placebo for tafenoquine on Day 1\*

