Population: Microbiologic-Intent-to-Treat

TTE6

Summary of recrudescence (blood stage failure) rates

	TQ+DHA-PQP (N=xx)	PQ+DHA-PQP (N=xx)	DHA-PQP only (N=xx)
Number of Subjects			
Recrudescence before Study Day 14	xx (xx%)	xx (xx%)	xx (xx%)
Censored	xx (xx%)	xx (xx%)	xx (xx%)
Recrudescence rate			
Estimate	xx%	xx%	xx%
95% CI	(xx%, xx%)	(xx%, xx%)	(xx%, xx%)
Difference from DHA-PQP only			
Estimated Difference	xx%	xx%	
95% CI	(xx%, xx%)	(xx%, xx%)	
Difference from PQ+DHA-PQP			
Estimated Difference	xx%		
95% CI	(xx%, xx%)		

Population: Microbiologic-Intent-to-Treat

EFF_T5

Analysis of Subjects with Relapse-Free Efficacy at 6 Months by CYP2D6 Metaboliser Class - Logistic Regression

Treatment Group Effect Tested	n	Number of Subjects Relapse Free	Adjusted Odds Ratio vs. EM+UM	90% CI	p-value
TQ+DHA-PQP					
Poor or Intermediate Metaboliser	xx	xx (xx%)	x.x	(x.x, x.x)	x.xxx
Extensive or Ultra Metaboliser	xx	xx (xx%)			
PQ+DHA-PQP					
Poor or Intermediate Metaboliser	xx	xx (xx%)	x.x	(x.x, x.x)	x.xxx
Extensive or Ultra Metaboliser	xx	xx (xx%)			
DHA-PQP only					
Poor or Intermediate Metaboliser	xx	xx (xx%)	x.x	(x.x, x.x)	x.xxx
Extensive or Ultra Metaboliser	xx	xx (xx%)			

Note: Model includes term for CYP2D6 Metaboliser Class. Metaboliser class is determined from the CYP2D6 activity score (AS) as follows: Poor AS=0; Intermediate AS=0.5 or 1; Extensive AS=1.5 or 2; Ultra AS≥2. A value over 1 represents benefit over the Extensive Metaboliser + Ultra Metaboliser group.

Population: Microbiologic-Intent-to-Treat

EFF_T6
Summary of P.vivax Gametocyte Emergence

	TQ+DHA-PQP (N=xx)	PQ+DHA-PQP (N=xx)	DHA-PQP only (N=xx)	Total (N=xx)
n	Xx	xx	xx	xx
Number of subjects with emergent gametocytes post-baseline	xx (xx%)	xx (xx%)	xx (xx%)	xx (xx%)

Note: Subjects who had P.vivax gametocytes at baseline are not included.

Population: Microbiologic-Intent-to-Treat

Table EFF_T7

Summary of Covariate and Treatment*Covariate Interaction Significance For Cox Proportional Hazards Model

Terms in the model	Degrees of Freedom	Wald Chi-Square	p-value
Battalion	xx	x.xx	x.xxx
Treatment*Battalion	xx	x.xx	x.xxx
Baseline Asexual Parasite Count	xx	x.xx	x.xxx
Treatment*Baseline Asexual Parasite Count	xx	x.xx	x.xxx

Model fitted first with covariate and treatment, then with covariate, treatment and treatment by covariate interaction

Population: Microbiologic-Intent-to-Treat

Table EFF_T8

Effect of CYP2D6 Activity Score (AS) on Relapse-Free Efficacy at 6 Months - Logistic Regression

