	Degrees of Freedom	Wald Chi-Square	p-value
<hr/>			
CYP2D6 Activity Score [1]			
DHA-PQP Only	xx	x.xx	x.xxx
TQ+DHA-PQP	xx	x.xx	x.xxx
PQ+DHA-PQP	xx	x.xx	x.xxx

[1] Model fitted with CYP2D6 Activity Score + battalion separately for each Treatment.
Note: p-value from a 2-sided test presented.

Population: Microbiologic-Intent-to-Treat

Table EFF_T9

Number (%) of Subjects Within Each CYP2D6 Metaboliser Class

CYP2D6 Metaboliser Class	TQ+DHA-PQP (N=xx)	PQ+DHA-PQP (N=xx)	DHA-PQP only (N=xx)
Poor Metaboliser	xx (xx%)	xx (xx%)	xx (xx%)
Intermediate Metaboliser	xx (xx%)	xx (xx%)	xx (xx%)
Extensive Metaboliser	xx (xx%)	xx (xx%)	xx (xx%)
Ultra Metaboliser	xx (xx%)	xx (xx%)	xx (xx%)

Metaboliser class is determined from the CYP2D6 activity score (AS) as follows: Poor AS=0; Intermediate AS=0.5 or 1; Extensive AS=1.5 or 2; Ultra AS≥2.5.

Population: Microbiologic-Intent-to-Treat

Table EFF_T10

Summary of the Number of Relapses per Subject

	TQ+DHA-PQP (N=xx)	PQ+DHA-PQP (N=xx)	DHA-PQP only (N=xx)
Number of Relapses			
n	xx	xx	xx
0	xx (xx%)	xx (xx%)	xx (xx%)
1	xx (xx%)	xx (xx%)	xx (xx%)
2	xx (xx%)	xx (xx%)	xx (xx%)
3	xx (xx%)	xx (xx%)	xx (xx%)

CONFIDENTIAL

200894

Population: Safety

Table SAFE_T1
Summary of Chemistry Data Outside the Reference Range

Lab Test: <Parameter (units)>

Timepoint	Clinical Concern Category	TQ+DHA-PQP (N=xx)	PQ+DHA-PQP (N=xx)	DHA-PQP only (N=xx)
Day 1	n	xx (xx%)	xx (xx%)	xx (xx%)
	Low	xx (xx%)	xx (xx%)	xx (xx%)
	High	xx (xx%)	xx (xx%)	xx (xx%)
Day 3	n	xx (xx%)	xx (xx%)	xx (xx%)
	Low	xx (xx%)	xx (xx%)	xx (xx%)
	High	xx (xx%)	xx (xx%)	xx (xx%)
...				
Any Time On-treatment	n	xx (xx%)	xx (xx%)	xx (xx%)
	Low	xx (xx%)	xx (xx%)	xx (xx%)
	High	xx (xx%)	xx (xx%)	xx (xx%)

CONFIDENTIAL

200894

Population: Safety

SAFE_T2
Summary of Categories of Change from Baseline Haemoglobin (G/L) Data by Treatment and Time

Treatment	N	Visit	Haemoglobin drop	n	Mean	SD	Median	Min	Max
TQ+DHA-PQP	xx	Day 3	<=20 g/L	xx	xxx.x	xxx.xx	xxx.x	xx	xx
			>20 g/L to <=30 g/L	xx	xxx.x	xxx.xx	xxx.x	xx	xx
			>30 g/L	xx	xxx.x	xxx.xx	xxx.x	xx	xx
			<=20 g/L	xx	xxx.x	xxx.xx	xxx.x	xx	xx
			>20 g/L to <=30 g/L	xx	xxx.x	xxx.xx	xxx.x	xx	xx
			>30 g/L	xx	xxx.x	xxx.xx	xxx.x	xx	Xx

CONFIDENTIAL

200894

Population: Safety

SAFE_T3
Summary of Haemoglobin Declines over first 28 days

	TQ+DHA-PQP	PQ+DHA-PQP	DHA-PQP only	Total
Maximum decline from baseline				
<=20 g/L	xx (xx%)	xx (xx%)	xx (xx%)	xx (xx%)
>20 g/L to <=30 g/L	xx (xx%)	xx (xx%)	xx (xx%)	xx (xx%)

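### The protocol's CYP2D6 hypothesis is a primaquine-versus-tafenoquine contrast, but the SAP fits only within-arm models and never estimates that contrast

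*SAP*

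**What the plan says.** Protocol 4.1 (Overall Design) announces the analysis as follows: "Exploratory CYP2D6 genotype analyses will be undertaken to test the hypothesis that null and/or intermediate metabolizers of 8-aminoquinoline drugs are more at risk of" recurrent malaria. The same bullet then limits the expected excess to one of the two drugs: "relapse with PQ but not TQ". The objectives tables in protocol section 3 and SAP 2.2 are looser. They ask about the relationship between CYP2D6 genotype and relapse risk, with percentage relapsing by genotype as the endpoint.

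SAP 7.3.5 plans two analyses.

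- **Metabolizer class** (poor plus intermediate against extensive plus ultra). Logistic regression, "models fitted separately for each treatment arm", with a "One-sided test at the 5% significance level". Each arm gets counts, an odds ratio, a 90% CI and a p-value. The EFF_T5 footnote agrees on the model: "Note: Model includes term for CYP2D6 Metaboliser Class".
- **Activity score (AS).** Again one logistic model per arm. The output is "Degrees of freedom, wald chi-square and p-value of the type III effect of AS in the model". The EFF_T8 footnote reads "Model fitted with CYP2D6 Activity Score + battalion separately for each Treatment", whereas the 7.3.5 text names activity score only.

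Neither shell has a between-arm row, and 7.3.5 plans no subgroup or sensitivity analysis for either. The treatment-by-covariate interactions in the SAP (battalion, baseline parasite count, weight; section 7.1.5.1) belong to the primary endpoint.

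**The concern.** An effect with one drug but not the other is a statement about the difference between two CYP2D6 effects. The planned output gives the two effects separately and never their difference. A reader who wants to address the protocol's hypothesis has only the separate arm results to compare, and the difference between a significant and a non-significant result need not itself be significant.

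The planned numbers make this matter. Each active arm expects about 7.5 relapses, so each within-arm test has low power, and a non-significant TQ result is weak evidence that CYP2D6 does not matter for TQ. At stake is an exploratory statement that TQ, unlike PQ, does not depend on CYP2D6 status.

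**Working it through.** **Inputs from the documents.** Protocol 9.2.1: 50 subjects per arm, 10% withdrawal (45 evaluable), relapse-free efficacy 50% / 85% / 85%. SAP 7.3.5: one-sided 5% test within each arm.

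**Assumed, because the documents do not give them.** Poor-plus-intermediate share 20-40%; CYP2D6 odds ratio (OR) for relapse of 1 to 6.

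**1. The plan's own figures.** Expected relapses: 50×0.50 + 50×0.15 + 50×0.15 = 25 + 7.5 + 7.5 = 40, and 40/150 = 26.7%, as stated. For the primary comparison, HR = ln 0.85 / ln 0.50 = 0.234, and events among 45 per arm = 45×(0.50 + 0.15) = 29.25. The Freedman log-rank form gives Φ(√29.25 × (1−0.234)/(1+0.234) − 1.96) = 91.8%. Two proportions at 45 per arm give 95.6%. The stated power above 90% is reproduced. No power is stated for the CYP2D6 analysis; these figures only fix its arm size and event rate.

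**2. How often PQ is significant and TQ is not when the CYP2D6 effect is the same in both.** Class-specific relapse rates were set so that each arm averages 15%. For example, with a 30% share and OR 3, they are 25.8% and 10.4%: 0.3×25.8 + 0.7×10.4 = 15.0. In each simulated arm, log OR = ln(ad/bc), SE = √(1/a+1/b+1/c+1/d), and the arm is significant if log OR/SE > 1.645. Arms with a zero cell count as not significant. The interaction statistic is z = (log OR_PQ − log OR_TQ)/√(SE²_PQ + SE²_TQ), tested two-sided at 5%. Results for n = 50 over shares of 20-40%:

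| True OR, same in both arms | PQ significant, TQ not |
|---|---|
| 1 (no effect) | 4-5% |
| 2 | 14-16% |
| 3 | 21-23% |
| 6 | 23-25% |

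At OR 3 and OR 6 the interaction test rejects in 1-3% of trials. That comparison is not like for like: the within-arm rule is one-sided, and the interaction test is conservative with so few events. Adding 0.5 to each cell of a table with a zero gives 22-23% at OR 3 and at OR 6. With 45 per arm the range over those two odds ratios is about 19-25%. Across these variants, within-arm power at OR 3 is only about 27-38%.

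**3. One illustrative data set** (assumed 20 poor/intermediate and 30 extensive/ultra per arm, 7 relapses per arm).

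- PQ: 5/20 against 2/30. OR = (5×28)/(15×2) = 4.67, 90% CI 1.07-20.4, one-sided p = 0.043.
- TQ: 4/20 against 3/30. OR = (4×27)/(16×3) = 2.25, 90% CI 0.58-8.76, one-sided p = 0.16.
- PQ:TQ ratio of odds ratios = 4.67/2.25 = 2.07, 90% CI 0.28-15.4, two-sided p = 0.55.

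The separate results look like PQ but not TQ. The contrast shows that the data cannot separate the drugs.

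**4. What the contrast can deliver.** If the hypothesis is true with PQ OR 5 and TQ OR 1, the two-sided interaction test has 10-15% power when zero-cell arms are set aside and 16-21% with the 0.5 correction. A single arm has a zero cell in about 4-19% of trials at OR 2-6 (n = 50 or 45), and ordinary maximum likelihood then fails.

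**The case against.** The best defence is that the analysis fits its stated objective. The objectives tables ask only for a relationship between genotype and relapse risk, and within-arm estimates answer that. The between-drug wording sits in one design bullet that itself opens as exploratory. This stands, and it limits the severity. It does not remove the mismatch, because that bullet says the hypothesis will be tested.

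A reader might infer that the SAP intends to compare p-values across arms and conclude that the drugs differ. The documents do not say so. Section 7.3.5 gives no rule for comparing arms, and EFF_T5 shows counts, odds ratios and 90% CIs beside the p-values. The risk is that the output can be misread, not that the plan prescribes the misreading.

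A reader might also take the pattern for a frequent false positive out of nothing. It is not: with no CYP2D6 effect it appears in 4-5% of trials. The larger figures need a real effect shared by both drugs, and the documents neither support nor exclude an effect of that size under TQ.

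Two further readings fail. The one-sided level is justified in 7.3.5 by PQ data and applied to all three arms, but it agrees with the 90% CI, and EFF_T8 gives two-sided p-values. Restricting it to PQ would be a preference, not a correction. The battalion discrepancy concerns only the activity score model; for metabolizer class, the text and EFF_T5 agree.

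**Conclusion.** The point holds as a minor one on an exploratory endpoint. The protocol states a PQ-versus-TQ hypothesis, and the SAP estimates nothing that addresses it directly. Under an identical effect in both arms, the misleading pattern would appear in roughly one trial in seven at OR 2 and nearly one in four at OR 3 to 6. These sizes rest on the protocol's 15% relapse rate and 50 per arm, and on class shares and odds ratios that are assumptions. They do not show that such a misreading will occur, and nothing here affects the primary or secondary efficacy conclusions.

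**What to change.** In SAP 7.3.5, add one logistic model with treatment, metabolizer class and treatment-by-class interaction. Use Firth or exact estimation because of the zero cells. Report the PQ:TQ ratio of odds ratios with its confidence interval, at a level stated in advance, as an exploratory estimate. State its direction, since EFF_T5 is framed on relapse-free outcome. Keep the within-arm results as descriptive, and add a sentence to the text and the EFF_T5 footnote that they do not by themselves establish a PQ-TQ difference.

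Separately, reconcile whether battalion is in the activity score model (7.3.5 text against the EFF_T8 footnote).

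The cost is one extra model, one table row and some wording, with no new data or subjects. The drawback is imprecision: with about 10-21% two-sided power at PQ OR 5 and TQ OR 1, the interval will be wide, and the report should say that a null result here is uninformative.
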